Standing or walking with several lifting or carrying activities	
Strenuous physical activities	

Gaussian distributed data is presented as means ± SD, otherwise as medians with interquartile range.

Lower extremity clinical group definition:

Upper extremity clinical group definition:

Spinal clinical group definition:

Statistical Analysis Plan

Analysis

Outcome definitions

Primary outcome

Short Musculoskeletal Function Assessment (SMFA)

Scores for the SMFA is divided in a dysfunction index SMFA-D and a bother index SMFA-B.

Assessing

Functional status.

Instrument / equipment

Self-reported
Questionnaire

Secondary outcome

Short Form 36 (SF-36)

Health-related quality of life.

Self-reported
Questionnaire

Other outcome measures

The New Mobility Score (NMS): composed score of physical mobility. Each question is scored between 0-3 points, depending on the degree of walking aid is used. help. The total possible score is between 0 and 9 points. Higher scores indicate better mobility.

Walking function inside, outside, and during shopping. Including whether a walking aid is used.

Self-reported
Questionnaire

PRISMA-7: composed score of frailty - each question scores either 0 or 1 points. The total possible score is between 0 and 7 points. Lower scores indicate less frailty.

Frailty/risk of frailty.

Self-reported
Questionnaire

Statistical Analysis Plan

Tilburg Frailty Indicator (TFI): bio-psycho-social approach, which measures frailty. It is composed of 15 multidimensional questions, regarding the physical, psychological, and social aspects of human functioning. Scoring range is between 0-15 points.
	
Frailty/risk of frailty.
	
Self-reported Questionnaire

A survey with self-formulated questions regarding name, sex, personal ID (CPR number), educational level, the region of pain the last three months (marked on a body chart), pain intensity and pain duration at the most painful body region the last three months, and physical activity level.
	
Musculoskeletal pain (region of pain, intensity of pain, duration of pain), physical activity level and demographic information.
	
Self-reported Questionnaire

Weight
	
Weight in kilograms.
	
Tanita 9MC-780U Multi Frequency Segmental Body Composition Analyzer (Tanita, Tokyo, Japan)

Height
	
Height in meters.
	
Etopoo stadiometer (China)

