2-minute walk test	Gait speed and distance. Gait speed will be calculated by dividing the covered distance with the time in seconds. Heart rate (in BPM) and perceived exertion (BORG 6-20) are collected pre- and post-testing.	Course 15.2 meters Stopwatch Apple Watch series 5 The Borg Rating of Perceived Exertion 6-20 scale
Timed Up and Go test (TUG)	Time noted in seconds on how long it takes to get up from a chair, walk three meters, turn around and go backheight) to the chair and sit down again.	Course 3 meters Chair (46 centimeters in height) with armrests Stopwatch
Tandem test	Static balance Balance is tested in three positions for ten seconds each (feet together,	Stopwatch

Statistical Analysis Plan

semi tandem, and full tandem). Time is noted in seconds for how long the participant can stand in each position.

Balance test and reaction test for upper and lower extremities

Balance test:

Fysiometer software

Velocity of the center of pressure in (Brønderslev, Denmark)

mm/sec.

Nintendo Wii Balance Board

Ellipse area for the center of

(Kyoto, Japan)

pressure in mm².

Reaction test:

Average reaction time in milliseconds

(ms) of seven reaction tests.

Food interviews

Intake of total energy intake and

Vitakost software

macronutrients based on 24-hour

(Kolding, Denmark)

dietary recall interviews.

History of falls

Interview regarding history of fall

Interview

within the last year

Statistical Analysis Plan

Analysis methods

- For objective 1:

- Under the assumption of normally distributed data, Pearson correlation coefficients will be calculated and presented with p values and 95%CI. Otherwise as Spearman's rank order correlation coefficients.
- Correlations will be conducted between SMFA-D/SMFA-B and measures on different ICF levels:
 - SMFA-D/SMFA-B and clinical measures (*upper extremity strength, lower extremity strength, body composition, gait test, TUG test, balance tests, reaction tests*).
 - SMFA-D/SMFA-B and other questionnaires (*SF36 health survey, Tilburg Frailty Indicator, PRISMA-7, and NMS*).
- Cronbach's alpha will be calculated to investigate the internal consistency of the specific categories of the SMFA (*daily activities, emotional status, arm and hand function category, mobility*). Cronbach's alpha above .70 are usually acceptable(5).
- Under the assumption of acceptable Cronbach's alpha values, same correlations will be conducted between specific categories of the SMFA and the different levels of ICF.

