- Under assumption of normally distributed data, two tailed unpaired t-tests will be conducted to investigate differences in SMFA-D/SMFA-B scores and presented baseline characteristics. Otherwise, a Mann-Whitney U test will be conducted.

- For objective 2:

- Under the assumption of normally distributed data, summary statistics will be presented as means with standard deviations, otherwise as medians with interquartile ranges. Categorical data will be presented with counts and percentages.
- Summary statistics will be presented for the total sample and for each clinical group.

- For objective 3:

- Under the assumption of normally distributed data, linear regression models will be conducted to investigate whether handgrip strength can be a predictor/proxy of upper extremity strength. Otherwise, quantile regression models will be conducted.

Statistical Analysis Plan

- Upper extremity strength measures (elbow extension, elbow flexion, shoulder abduction) will be set as the dependent variable and hand grip strength of the same arm as the predictor variable. Other explanatory variables to be fitted in the model will be: *age, gender, and height* since these variables affect hand grip strength(6). Other variables added in the model are the fat free mass and knee extension strength(7).

Hypothesis

- SMFA-D and SMFA-B are strongly correlated with each other(8).
- SMFA-D and SMFA-B scores are fair to moderately negatively correlated with the following clinical measures: handgrip strength, MVIC of knee extension, tandem balance test, 2-minute walk test, Leg press strength, knee extension strength and calf extension strength. Further, we hypothesize that the SMFA-D will show higher negative correlations with mentioned clinical measures than the SMFA-B (8).
- SMFA-D and SMFA-B are moderate to highly correlated with other health-related questionnaires and frailty indicators: SF36 (negative association), Tilburg Frailty Indicator (positive association), PRISMA7 (positive association) and NMS (positive association) (9, 10).
- We hypothesize that specific functional areas on the SMFA will not be as strongly related to the sum score of SMFA as they will be to a specific category (8).
- We anticipate low physical and functional scores of the total sample (11).
- Handgrip strength is a good proxy of upper extremity strength (elbow extension, elbow flexion and shoulder abduction)(12).

Missing data

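### The predicted positive SMFA–NMS association contradicts the SAP's own NMS scoring and its other predicted signs

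*SAP*

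**What the plan says.** Two parts of the SAP bear on this.

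**Outcome definitions.** NMS runs from 0 to 9 points, and "Higher scores indicate better mobility". PRISMA-7 runs from 0 to 7 points, and "Lower scores indicate less frailty". For the primary outcome the SAP says only "Scores for the SMFA is divided in a dysfunction index SMFA-D and a bother index SMFA-B". It gives no scoring direction for SMFA; the Missing data section refers to the published scoring instructions. No direction is stated for SF-36 or the Tilburg Frailty Indicator.

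**Hypothesis.** For performance tests: "SMFA-D and SMFA-B scores are fair to moderately negatively correlated with the following clinical measures". Seven are then listed: handgrip, isometric knee extension (MVIC), tandem balance, 2-minute walk, leg press, knee extension and calf extension. For questionnaires, with correlations expected to be moderate to high, the signs are "SF36 (negative association), Tilburg Frailty Indicator (positive association") and then "PRISMA7 (positive association) and NMS (positive association) (9, 10").

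The correlation of SMFA-D and SMFA-B with NMS is among the planned analyses for objective 1 (Analysis methods).

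**The concern.** High NMS is a good result and high PRISMA-7 is a bad one, yet SMFA is predicted to rise with both. If SMFA tracks function in a consistent direction, one of the two signs must be wrong.

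The sign matters because objective 1 is a construct-validity question, and the signed expectations are what the observed correlations will be compared with. As written, a negative SMFA–NMS correlation, which is what a valid SMFA should give if higher is worse, contradicts the plan. An anomalous positive one agrees with it. If the sign were changed without comment when the results are reported, it would look like a hypothesis altered after the data were seen.

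**Working it through.** **Inputs, all from the SAP.** The predicted signs come from the Hypothesis section. The directions of NMS and PRISMA-7 are stated in the outcome definitions. The directions of the seven performance tests follow from what is recorded: force, torque or load for the strength tests; distance and gait speed for the 2-minute walk; and, for tandem balance, "Time is noted in seconds for how long the participant can stand in each position". More is better on each. One inference is involved: the 2-minute walk also yields heart rate and perceived exertion, and I take distance or speed as the intended result.

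**Rule.** Code each comparator +1 if higher is better and −1 if higher is worse. Multiply by the predicted sign. The product is the SMFA direction that the prediction implies (+1: higher SMFA is better; −1: higher SMFA is worse).

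| Comparator | Direction | Predicted sign | Implied SMFA direction |
|---|---|---|---|
| Handgrip strength | +1 | −1 | −1 |
| Knee extension MVIC | +1 | −1 | −1 |
| Tandem balance | +1 | −1 | −1 |
| 2-minute walk | +1 | −1 | −1 |
| Leg press | +1 | −1 | −1 |
| Knee extension | +1 | −1 | −1 |
| Calf extension | +1 | −1 | −1 |
| PRISMA-7 | −1 | +1 | −1 |
| NMS | +1 | +1 | **+1** |

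**Count.**
- If higher SMFA is worse, 8 of 9 predictions fit and 1 (NMS) does not.
- If SMFA is reversed, 1 of 9 fits (NMS) and 8 do not.
- SF-36 and the Tilburg Frailty Indicator are left out because the SAP states no direction for them.
- Measures with a signed expectation: 7 clinical + 4 questionnaires = 11. Affected: 1/11 = 9.1% of all, and 1/4 = 25% of the questionnaires. These count named measures, not the correlations that will be computed.

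The index names, dysfunction and bother, point the same way as the eight agreeing rows. The sharpest contrast lies within one domain: SMFA is predicted to fall as 2-minute walk performance improves, yet to rise as self-reported walking mobility on NMS improves.

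**What does not change.** The sample size depends only on the absolute value of the correlation: n = ((z₀.₉₇₅ + z₀.₈₀)/atanh(0.3))² + 3 = ((1.960 + 0.842)/0.3095)² + 3 = 84.93, rounded up to 85. This reproduces the SAP's figure, and it was set for the SMFA–SF-36 pair, not NMS. Estimates, confidence intervals and two-tailed p values do not depend on the predicted sign. The expectation "SMFA-D and SMFA-B are strongly correlated with each other" and the one on functional areas against the sum score carry no sign and are unaffected.

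**The case against.** **Both signs could hold mathematically.** Two measures that are inversely related to each other can each correlate positively with a third. If both correlate with SMFA at r, the correlation between them must be at least r² − (1 − r²) = 2r² − 1. At r = .50, the bottom of the SAP's moderate band, that bound is −.50, so the pair of predictions is possible. At r = .75, where the strong band begins, it is +.125, and greater mobility would have to go with greater frailty. This part of the objection stands: the prediction is incoherent as a construct-validity expectation, but it is not impossible over the whole predicted range.

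**Positive might mean favourable, or NMS might be recoded.** The first reading fails because PRISMA-7, where higher is frailer, is also labelled positive. The second has no support in the SAP, which gives a 0–9 score with higher better and mentions no reversal.

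**The consequence is small.** This also stands. The SAP has no rule for counting hypotheses as confirmed and no threshold for declaring construct validity. NMS is listed among the other outcome measures, and its direction is printed, so a careful reader can see the slip. What is at stake is how one result is interpreted.

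**SMFA direction may be left to its scoring instructions.** That is fair, and its absence is not counted as an error here. It does mean that the conclusion that higher SMFA is worse is inferred.

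**Conclusion.** The contradiction is real and lies within the SAP: the NMS sign does not fit the stated NMS scoring together with the other eight predictions whose direction can be read. The expectation consistent with them is negative for both SMFA-D and SMFA-B.

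This rests on three assumptions: that higher SMFA means worse function, as the SAP implies but does not state; that mobility and frailty are expected to oppose each other; and that NMS is analysed as scored in the outcome definitions. The point is minor. It affects how one pre-specified hypothesis is read and no number in the plan.

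**What to change.** In the Hypothesis section, change the NMS sign to negative for SMFA-D and SMFA-B. If NMS is in fact reverse-scored for the analysis, keep the sign, say so, and reconcile the NMS entry in the outcome definitions.

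It would also help to add one sentence giving the SMFA scoring direction as set out in the scoring instructions, so that every predicted sign can be checked from the SAP alone.

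Record the change as a dated correction. Version 1 of the SAP is dated December 2021, after recruitment ran from January to September 2021, so the note should say whether the SMFA–NMS correlation had already been examined.

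The cost is one word (or one sentence on NMS scoring), one sentence on SMFA direction and one dated line. No new data or analysis is needed.
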